7 PLANNED ANALYSES

Disposition of the patient population participating in the trial will be analysed by treatment groups and presented in the clinical trial report as a frequency-distribution.

The number of patients participating (screened, randomised, screened but not randomised, etc.) in the study by region, country and, for treated patients, centre, will also be analysed by treatment group and presented as a frequency distribution. The reason for not randomising screened patients will also be summarised. See [Table 9.1: 1](#) for assignment of countries within region.

In addition, the number of patients who discontinued trial medication due to fatal and non-fatal adverse events will be displayed in Appendix 16.1.9.2, as well as the number of screened patients by country and the number of screened patients by age groups. These analyses will be done for public data disclosure on European Union Drug Regulating Authorities Clinical Trials (EudraCT).

A summary of the number of patients in each randomisation stratum per treatment will also be shown. This summary will be based upon the data received from the IxRS provider.

For efficacy analyses, patients will be analysed according to the stratum to which they belong (regardless of any mis-assignment based on identification of the wrong stratum). For patients who were mistakenly randomised on both MDI and CSII at baseline, the stratification factor from IxRS will be used.

A frequency of patients with IPVs, also summarised by whether the IPV led to exclusion from the PPS, will be presented by treatment group for the randomised set. The frequency of patients in different analysis sets will also be analysed for each treatment group.

For in-text tables presenting descriptive analysis of the endpoints and other variables (analysed in original scale), the set of summary statistics is: N (number of patients with non-missing values), mean, standard deviation (SD).

For End-Of-Text (EoT) tables, the set of summary statistics is: N (number of patients with non-missing values) / Mean / SD / standard error (SE) / Min / Q1 (lower quartile)/ Median / Q3 (upper quartile)/ Max.

For the in-text, end-of-text and appendix tables presenting descriptive analysis of the endpoints and other variables (analysed on logarithmic scale), the respective summary statistics (e.g., gMean, gCV, etc.) will be used.

Statistical parameters will be displayed to a defined number of decimal places as specified in the BI guideline "Reporting of Clinical Trials and Project Summaries" ([7](#)).

Tabulations of frequencies for categorical data will include all possible categories and will display the number of observations in a category as well as the percentage (%) relative to the respective treatment group (unless otherwise specified, all patients in the respective patient set whether they have non-missing values or not). Percentages will be rounded to one decimal place. The category missing will be displayed only if there are actually missing values.

Treatment comparison

In all specified statistical analyses, treatment comparisons will be made between each randomised Empagliflozin group (2.5, 10 and 25 mg) and placebo.

7.1 DEMOGRAPHICS AND OTHER BASELINE CHARACTERISTICS

7.1.1 Baseline evaluation

Descriptive analysis of the following demographic variables measured at baseline will be presented:

Sex, race, ethnicity, region, age (years), age-groups, BMI (kg/m²) categories, height (cm), smoking history and alcohol status, time since diagnosis of diabetes (years) (continuous and in categories), eGFR by CKD-EPI creatinine equation (continuous and in categories) and eGFR by CKD-EPI creatinine-cystatin C (continuous and in categories).

See [Section 7.8.2.4](#) for details on the derivation of eGFR endpoints.

Descriptive analysis of the following variables measured at baseline will be presented:

HbA1c (%) (continuous and in categories), FPG (mg/dL) (continuous and in categories), weight (kg) (continuous and in categories), waist circumference (cm), blood pressure (mmHg) (continuous and in categories), UACR (mg/gcrea) (continuous and in categories), fasted serum BHB (mmol/L) (continuous and in categories), capillary daily patient self-measured BHB (mmol/L) (continuous and in categories) and capillary morning patient self-measured BHB (mmol/L) (continuous and in categories).

Baseline hypoglycaemia rates will be presented in a separate table, displaying both the rate (per 30 days) and the frequency (from day -28 to day -1, inclusive) of 'severe hypoglycaemia events confirmed by adjudication' and 'symptomatic hypoglycaemia AEs with confirmed plasma glucose <54mg/dL and/or severe hypoglycaemia events confirmed by adjudication'. For the rates, the statistics will include the number of patients overall (N), the number of patients with at least 1 event (Nh), mean, SD, SE, min, 5th percentile (P5), P10, P25, median, P75, P90, P95, and max.

[REDACTED]

Categories for baseline characteristics are defined in [Section 6.4](#).

Demographic and baseline characteristics tables will be presented on the FAS.

The demographic analysis will be repeated on the randomised population in Appendix 16.1.9.2 for disclosure on EudraCT.

[REDACTED]

[REDACTED]

[REDACTED]

- [REDACTED]
- [REDACTED]
- [REDACTED]
- [REDACTED]
- [REDACTED]
- [REDACTED]

[REDACTED]

[REDACTED]

[REDACTED]

[REDACTED]

[REDACTED]

[REDACTED]

7.2 CONCOMITANT DISEASES AND MEDICATION

Only descriptive statistics are planned for this section of the report using the FAS.

Concomitant medication use will be summarised by Anatomical-Therapeutic-Chemical classification level 3 (ATC3) and preferred name. Summaries will be presented for concomitant therapies taken during randomised treatment and those taken at baseline.

Separate summaries of use of antihypertensives, ASA or lipid lowering drugs at baseline by preferred name will be presented. The displayed categories and defining ATC levels and ATC codes are shown in [Table 9.2: 1](#).

Background pre-existing insulin therapy, including a categorisation of patients using MDI versus CSII will be presented. This summary will include background total daily insulin dose at baseline in insulin 'unit' and 'units/kg' as units of insulin per kg body weight at baseline. The table will also display the total daily basal insulin dose and the total daily bolus insulin dose at baseline. The number of insulin injections at baseline will be presented for MDI patients.

Concomitant diseases will be summarised by MedDRA System Organ Class (SOC) and preferred term (PT). Relevant diabetic medical history will also be presented by treatment group.

7.3 TREATMENT COMPLIANCE

Only descriptive statistics are planned for this section of the report.

Frequency distribution of patients with an overall compliance between 80% and 120% (inclusive) will be reported, as well as patients outside this range.

The overall compliance will be calculated as a weighted average of reported compliance. The sum of all reported compliance over the planned visits (disregarding of run-in) will be divided by the total duration (until last visit where medication is returned).

Refer to [Section 6.6.3](#) for how handling a single missing visit date for a compliance record, in the overall compliance calculation.

If compliance is missing at more than one on-treatment visit (>1), the overall compliance will be set to missing.

If a patient has a temporary treatment interruption, this should be reflected in the calculation of compliance.

If a patient prematurely discontinues from treatment, compliance will be calculated until last study drug intake. Missing compliance values for off-treatment visits will not be considered in the calculation for overall compliance.

The FAS patient set will be considered.

7.4 PRIMARY ENDPOINT

7.4.1 Primary analysis

The primary endpoint in this trial is the change from baseline in HbA1c (%) at 26 weeks. Efficacy and effectiveness will be tested in a hierarchical manner.

The primary efficacy analysis will be performed on the FAS (OC). Patients will be assigned to the treatment they were randomised to. Only on-treatment HbA1c values will be included

in the primary analysis. Only data up to the Week 26 timepoint will be included. All randomised treatment groups will be included in the same analysis.

Mean changes from baseline in HbA1c after 26 weeks will be analysed using a restricted maximum likelihood-based repeated measures approach (MMRM analysis). Analyses will include the fixed categorical effects of treatment, pre-existing insulin therapy, week and treatment by week interaction, as well as the continuous, fixed covariates of baseline HbA1c, baseline eGFR and baseline HbA1c by week interaction. Patient will be included as random effect. An unstructured (co)variance structure will be used to model the within patient measurements.

If this analysis fails to converge, the following covariance structures will be tested: first-order ante-dependence (ANTE(1)), heterogeneous Toeplitz (TOEPH), Toeplitz (TOEP) and first-order autoregressive (AR(1)). The (co)variance structure converging to the best fit, as determined by Akaike's information criterion, will be used as the primary analysis.

The Kenward-Roger approximation will be used to estimate denominator degrees of freedom. Significance tests will be based on least-squares means using a two-sided $\alpha = 0.025$ (two-sided 97.5% confidence intervals). The residuals are assumed to have a multivariate normal distribution with zero means and covariance matrix as specified above. The primary treatment comparisons will be the contrasts between active treatments and placebo at Week 26.

The statistical model will be:

HbA1c change from baseline = overall mean + continuous baseline HbA1c + pre-existing insulin therapy + continuous baseline eGFR + treatment + week + baseline HbA1c by week interaction + treatment by week interaction + random error

If the null hypothesis is successfully rejected for the efficacy analysis, then an effectiveness analysis will be performed on the mITT (OC-AD), including both on- and off-treatment data. The model will be the same as the model for the efficacy analysis described above.

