The randomisation will be stratified by the Visit 5 eGFR value (< $60 \text{ mL/min/1.73 m}^2$ versus $\geq 60 \text{ mL/min/1.73 m}^2$), the Visit 5 HbA_{1c} value (< 8.5% versus $\geq 8.5\%$), by the patients' pre-existing insulin therapy (MDI versus CSII), and by the patient's participation in the CGM substudy (CGM participation versus non-CGM participation). If necessary, and depending upon global distribution, entry of patients into a particular HbA_{1c} stratum may be capped.

Page 75 of 122

Proprietary confidential information © 2016 Boehringer Ingelheim International GmbH or one or more of its affiliated companies

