7.7 DETERMINATION OF SAMPLE SIZE

Based on previous experience with empagliflozin it is estimated that the change in HbA_{1c} from baseline after 26 weeks of treatment is 0.3% in empagliflozin (2.5 mg, 10 mg and 25 mg) and 0% in placebo and that the standard deviation of this difference is 0.9%.

As this trial investigates primarily the 2 higher dose levels of empagliflozin, 10 mg and 25 mg, the alpha (Type I error) is assumed to be 2.5%. Assuming that the change from baseline in HbA_{1c} follows a normal distribution (Student's t-test) and that a two-sided test will be employed, with equal standard deviations, then a sample size of 225 patients per arm will show superiority with a power of 90%.

Based on the results of these 2 tests (see Section 7.2 for further details), when comparing empagliflozin 2.5 mg (n=225) to placebo (n=225) on the primary endpoint, there is 82% power, respectively 76%, to detect a significant difference (alpha=1%, respectively alpha=0.5%) of 0.3% with a common standard deviation of 0.9%.

Software package nQuery version 7.0 was used to derive the sample size.

Given that there are 4 treatment groups, a total sample size of 960 patients (240 per group) will be randomised to allow for an estimated 6% of patients who do not qualify for the FAS.

Page 88 of 122

Proprietary confidential information © 2016 Boehringer Ingelheim International GmbH or one or more of its affiliated companies

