7.5 SECONDARY ENDPOINTS

7.5.1 Key secondary endpoints

7.5.1.1 Rate of symptomatic hypoglycaemic AEs with confirmed plasma glucose <54 mg/dL and/or severe hypoglycaemic events confirmed by adjudication

[figure not shown]
Confirmatory analysis

The analysis of the rate of symptomatic hypoglycaemic AEs with confirmed plasma glucose <54 mg/dL and/or severe hypoglycaemic events confirmed by adjudication will utilise a negative binomial model, with terms for treatment, continuous baseline rate, continuous baseline HbA1c, continuous baseline eGFR and pre-existing insulin therapy as fixed effects and log(time at risk) as an offset. The results will be presented as a rate per patient-year. This analysis will be performed on the FAS (OC).

The baseline rate of symptomatic hypoglycaemic AEs with confirmed plasma glucose < 54 mg/dL and/or severe hypoglycaemic events confirmed by adjudication will be calculated based on the event rate during the 4 weeks prior to randomisation, see [Section 6.7](#).

The analysis of the rate from Week 5 to Week 26 will include all on-treatment events from the start of Week 5 (Day 29) until one day after treatment stop date. This period will also define the time at risk.

The analysis of the rate from Week 1 to Week 26 will include all on-treatment events from the date of first study drug intake until one day after treatment stop date. This period will also define the time at risk.

[REDACTED]

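### CGM-substudy participation is a stratification factor but appears in none of the visible confirmatory models; adding it is a minor, free gain in precision

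*SAP*

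**What the plan says.** Protocol 7.1 and 7.6 name four stratification factors: eGFR (below 60 or not), HbA1c (below 8.5% or not), MDI versus CSII, and "participation in the CGM substudy (CGM participation versus non-CGM participation"). Protocol 3.1 puts about 30% of patients in the substudy, by choice, at selected sites with CGM experience. The first CGM period falls in the placebo run-in, so participation is settled before randomisation.

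The confirmatory models are all visible:

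- **HbA1c, efficacy and effectiveness** (Protocol 7.3.1.1, SAP 7.4.1): "Analyses will include the fixed categorical effects of treatment, pre-existing insulin therapy, week and treatment by week interaction", plus baseline HbA1c, baseline eGFR and baseline HbA1c by week. The printed model equation has the same terms, and the effectiveness analysis reuses the model.
- **Hypoglycaemia rates** (SAP 7.5.1.1): a negative binomial model "with terms for treatment, continuous baseline rate, continuous baseline HbA1c, continuous baseline eGFR and pre-existing insulin therapy as fixed effects", with log time at risk as offset.
- **Weight, insulin dose, SBP and DBP** (SAP 7.5.1.2 to 7.5.1.4): the primary MMRM pattern, with the endpoint's own baseline and its interaction with week.

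Insulin therapy enters every model as a factor, and HbA1c and eGFR enter as continuous covariates. CGM participation enters none, and the visible text gives no reason. SAP section 7 and Protocol 7.3.1.1 have efficacy patients analysed by their true stratum even if it was wrongly entered at randomisation. For CGM, no listed model has a term through which that rule could act.

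**The concern.** Stratified blocks force the arms to be balanced on CGM participation, so differences between participants and others hardly contribute to the true variability of a treatment contrast. A model without the factor still counts those differences as residual variance (MMRM) or dispersion (negative binomial). The reported standard error is then somewhat larger than the true one.

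The factor could be prognostic, because participants are selected twice: by site, and by their own choice together with the investigator's judgement that they can perform CGM. No confirmatory model has a centre or country term (SAP 6.5 describes centre effects only), so CGM participation is the one design variable that could pick up part of a site difference.

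What is at stake is power. The HbA1c contrasts open the testing sequence, and under Protocol 7.2 the hypoglycaemia tests carry nine-tenths of each dose's key-secondary alpha: 0.018 to 0.0225 once that dose has passed its own HbA1c tests.

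**Working it through.** **1. Inputs (Protocol 7.7 unless stated).** Effect: "0.3% in empagliflozin (2.5 mg, 10 mg and 25 mg) and 0% in placebo". SD: "the standard deviation of this difference is 0.9" (percentage points). Alpha: "the alpha (Type I error) is assumed to be 2.5" percent per high-dose comparison. Test: "a two-sided test will be employed, with equal standard deviations". Stated result: "a sample size of 225 patients per arm will show superiority with a power of 90" percent. CGM share 0.30 (Protocol 3.1).

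**2. The plan's own figure.** Normal approximation: n = 2 × (2.2414 + 1.2816)² × (0.9/0.3)² = 223.4, so 224 per arm. The noncentral t gives 225, with power 90.05%. Then 225/0.94 = 239.4, so 240 per arm and 960 in total. The stated size reproduces.

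**3. HbA1c.** Let d be the difference in HbA1c change between CGM participants and others that remains after adjustment for the other covariates. The documents give no value, so d is an assumption shown over a range. With the total SD held at 0.9, the share of variance due to the factor is

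R² = 0.3 × 0.7 × d² / 0.81.

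With the term in the model, the residual SD is 0.9 × √(1 − R²). Without it, the reported SE is too large by the factor 1/√(1 − R²), and the actual two-sided type I error is 2 × [1 − Φ(2.2414/√(1 − R²))].

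| d | R² | SE excess without term | Power without | Power with | Actual type I error without (nominal 0.025) |
|---|---|---|---|---|---|
| 0 | 0 | 0 | 90.0% | 90.0% | 0.0250 |
| 0.1 | 0.0026 | 0.13% | 90.0% | 90.1% | 0.0248 |
| 0.2 | 0.0104 | 0.52% | 90.0% | 90.4% | 0.0242 |
| 0.3 | 0.0233 | 1.2% | 90.0% | 90.8% | 0.0233 |

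At d = 0.3 the stratum difference is already as large as the assumed drug effect.

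**4. Simulation check at d = 0.3.** 20,000 null trials with stratified blocks, 900 patients in four arms, two arms compared. Mean SE was 0.0848 without the term and 0.0838 with it, against an empirical SD of the estimate of 0.0840. Rejection rates were 0.0233 and 0.0254 (Monte Carlo standard error √(0.025 × 0.975/20,000) = 0.0011). At d = 0 the two models agree.

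**5. Hypoglycaemia.** The plan gives neither an event rate nor a dispersion. Assumed ranges: λ = 2 to 10 events per patient-year, dispersion k = 0.5 to 2, T = 22/52 year, 225 per arm, and a rate ratio R between CGM participants and others. Let m be a stratum's expected count and μ the overall one.

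- With the term: SE = √(2/Σw), where w = 225 × share / (1/m + k) for each stratum.
- Without it: SE = √(2V/(225μ²)), where V = μ + k·E[m²] + (E[m²] − μ²).

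Example, λ = 5, k = 1, R = 1.5: m = 1.84 and 2.76, μ = 2.115. With the term, w = 102.0 and 49.5, so SE = 0.1149. Without it, E[m²] = 4.653 and V = 6.946, so SE = 0.1175, which is 2.3% larger. Over the whole grid the excess is 0.4% to 1.0% for R = 1.25, 1.3% to 3.6% for R = 1.5, and 4% to 11% for R = 2.

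These figures leave out the patient's own baseline rate, which the planned model includes. They therefore overstate the loss to the extent that baseline rates already carry the stratum difference.

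**The case against.** The strongest reply is that this hardly matters. The effect is conservative, and a visible gain for HbA1c needs a substudy flag to shift HbA1c by about as much as the drug is assumed to. That stands, and it sets the weight of the point.

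A reader might infer that the standard errors are invalid, that the type I error is inflated, or that the estimates are biased. None of this is supported. Participation is fixed before randomisation and balanced by design, so omitting it does not shift the treatment contrast, and the error rate stays at or below nominal.

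A reader might also infer that wearing the trial CGM changes hypoglycaemia counts. The documents point the other way. The trial CGM is blinded (Protocol 4.2.2.2), the glucose values behind the hypoglycaemia criteria come from the SBGM device and the central laboratory (Protocol 5.3.5.1), and insulin decisions rest on SBGM or laboratory values (Protocol 5.3.2.1). What remains is a possible difference between sites or volunteers. The baseline rate over the four weeks before randomisation would absorb part of a stable difference of that kind.

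Nor can it be said that no model anywhere adjusts for CGM participation. Parts of SAP 7.4 and 7.5 are redacted, and a sensitivity analysis with the term may lie there. The statement covers only the visible confirmatory models.

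**Conclusion.** The point holds as a free improvement of minor weight. CGM participation is the only stratification factor with no counterpart in the visible confirmatory models.

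For HbA1c, the cost of leaving it out is less than one percentage point of power if the adjusted difference between participants and others is 0.1 to 0.3 points, and nothing if there is no difference. This rests on an assumed difference, a 30% share, and treating Week 26 as a two-group comparison, as the plan's own sample size does. For hypoglycaemia the loss may be larger, but its size cannot be fixed from the documents.

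**What to change.** Add CGM-substudy participation (yes/no) as a fixed effect in the confirmatory models of SAP 7.4.1 (efficacy and effectiveness) and 7.5.1.1 to 7.5.1.4. Code it by the patient's true stratum, following the rule in SAP section 7. Coding it strictly as entered at randomisation would conflict with that rule.

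The cost is one line per model and one degree of freedom, and the factor is already collected for randomisation. The change should be made before unblinding, so that it cannot look data-driven. The sample size need not change. Nor need the safety models, because the loss described concerns confirmatory tests and Protocol 7.3.4 plans no hypothesis testing for safety.

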7.3.1 Primary endpoint analyses

7.3.1.1 Primary analysis of the primary endpoint

The primary endpoint in this trial is the change from baseline in HbA_{1c} (%) after 26 weeks.

The primary efficacy analysis will be performed on the FAS; patients will be assigned to the treatment they were randomised to and analysed according to the stratum to which they belong (regardless of any mis-assignment based on identification of the wrong stratum). Only on-treatment HbA_{1c} values will be included in the primary analysis for efficacy.

Mean changes from baseline in HbA_{1c} after 26 weeks will be analysed using a restricted maximum likelihood-based repeated measures approach (MMRM analysis). Analyses will include the fixed categorical effects of treatment, pre-existing insulin therapy, week and treatment by week interaction, as well as the continuous, fixed covariates of baseline HbA_{1c} , baseline eGFR and baseline HbA_{1c} by week interaction. An unstructured (co)variance structure will be used to model the within patient measurements.

If this analysis fails to converge, the following covariance structures will be tested: compound symmetry, variance components and Toeplitz. The (co)variance structure converging to the best fit, as determined by Akaike's information criterion, will be used as the primary analysis.

The Kenward-Roger approximation will be used to estimate denominator degrees of freedom. Significance tests will be based on least-squares means using a two-sided $\alpha = 0.025$ (two-sided 97.5% confidence intervals). The residuals are assumed to have a multivariate normal distribution with zero means and covariance matrix as specified above. The primary treatment comparisons will be the contrast between treatments at Week 26.

The statistical model will be:

 HbA_{1c} change from baseline = overall mean + continuous baseline HbA_{1c} + pre-existing insulin therapy + continuous baseline eGFR + treatment + week + baseline HbA_{1c} by week interaction + treatment by week interaction + random error

For empagliflozin 10 mg and 25 mg, following the analysis of the efficacy estimand, an effectiveness analysis will be performed on the mITT set. This will use the same model as described for the efficacy analysis, but include all available on- and off- treatment values.

Proprietary confidential information © 2016 Boehringer Ingelheim International GmbH or one or more of its affiliated companies

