[3] Refer to a sensitivity analysis on elevated liver enzymes, for which events with an onset date up to 30 days after the study treatment stop will be included in the analysis.

Measurements taken after the last intake of study drug and after the end of the endpoint specific follow-up period will be considered off-treatment values.

Efficacy, safety, [REDACTED] will be assigned to visits based on time windows around the planned visit dates. These time windows are defined based on the planned number of days after the date of first administration of study drug (see [Table 6.7: 2](#)).

Table 6.7: 2 Time windows for HbA1c measurements at scheduled visits after randomisation

Visit number	Visit label	Planned days	Time window (actual days on treatment)	
			Start	End ^A
6	Baseline	0	NA	1 ^B
8	Week 4	28	2	56
9	Week 12	84	57	105
10	Week 18	126	106	154
11	Week 26	182	155	Study drug stop date + X days

^A In case of premature discontinuation of the study drug an eEOT visit has to be performed. Measurements from the eEOT visit will be assigned to the appropriate visit according to the table. In this case the time window for the visit that includes the eEOT visit will end X days after the study drug stop date, including Day X. The definition of X is endpoint specific, cf. [Table 6.7: 1](#). Patients will then be asked to continue in the study according to the visit schedule. Off-treatment measurements will be assigned to visits in the same manner. No time window for optional visit is planned.

^B Only values taken prior to the start of treatment with randomised study drug can be considered baseline values. Time windows will be used for assignment of measurements to scheduled visits.

The mid-point between two visits defines the end of a time window, with the midpoint being included in the time window of the preceding visit. The end of the time window of the last on-treatment visit (end of treatment (EoT)) is endpoint dependent (cf. [Table 6.7: 1](#)). As endpoints are planned to be measured according to different visit schedules, this midpoint algorithm will be applied and the time windows modified accordingly.

For example, the time windows for the blood pressure endpoints have been detailed in [Table 6.7: 3](#).

Table 6.7: 3 Time windows for blood pressure measurements at scheduled visits after randomisation

Visit number	Visit label	Planned days	Time window (actual days on treatment)	
			Start	End ^A
6	Baseline	0	NA	1 ^B
7	Week 1	7	2	17
8	Week 4	28	18	56

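### Does naming patient as a random effect alongside an unstructured covariance (SAP 7.4.1) put the primary HbA1c model at risk?

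*SAP*

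**What the plan says.** After listing the fixed effects of the repeated-measures model, SAP 7.4.1 continues: "Patient will be included as random effect. An unstructured (co)variance structure will be used to model the within patient measurements". The written-out equation a few lines later ends in "treatment by week interaction + random error", with no patient term. The same section assumes multivariate normal residuals that carry the covariance matrix just specified.

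The fallback reads: "If this analysis fails to converge, the following covariance structures will be tested: first-order ante-dependence (ANTE(1)), heterogeneous Toeplitz (TOEPH), Toeplitz (TOEP"), with AR(1) as the last candidate. Then: "The (co)variance structure converging to the best fit, as determined by Akaike's information criterion, will be used as the primary analysis". The effectiveness analysis inherits the model: "The model will be the same as the model for the efficacy analysis described above".

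Protocol 7.3.1.1 has the same fixed effects, the same equation and the same covariance, "An unstructured (co)variance structure will be used to model the within patient measurements", and no random patient effect.

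**The concern.** An unstructured matrix already uses every distinct variance and covariance among a patient's visits, so a random patient intercept has nothing left to explain. Taken literally, "Patient will be included as random effect" makes the covariance parameters non-unique and contradicts both the SAP's own equation and the protocol.

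Such a redundancy would normally be harmless, but here non-convergence has a consequence: an AIC-chosen restricted structure becomes the primary analysis, and plain unstructured is not among the listed candidates. If the software stopped on the singular information matrix, a wording slip and not the data would pick the confirmatory model. The efficacy test and the effectiveness test both use this model, and together they gate the 2.5 mg comparison and the key secondary endpoints.

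**Working it through.** **Inputs.** There are four post-baseline HbA1c visits, Weeks 4, 12, 18 and 26 (SAP 6.7, the table "Time windows for HbA1c measurements at scheduled visits after randomisation"). Protocol 7.7 gives a difference of 0.3, SD 0.9, two-sided alpha 0.025 and 225 per arm. Correlations, earlier-visit SDs and dropout are assumed below, because the documents do not give them.

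**The plan's own figure.** Neither document states a covariance parameter count. The planning figures used in the simulations do reproduce: the noncentral t gives 225 per arm with power 0.9005, then 225/0.94 = 239.4, rounded up to 240, and 4 × 240 = 960.

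**Parameter count.** Unstructured at four visits has 4 × 5/2 = 10 parameters. With a random intercept the marginal covariance is V = U + τ²J, where U is the unstructured matrix, τ² the patient variance and J the all-ones matrix. For any constant c, the pair (U − cJ, τ² + c) gives the same V. One parameter is therefore redundant whatever the data. A numerical rank check gives:

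| Structure | Parameters / rank alone | With a patient intercept |
|---|---|---|
| Unstructured | 10 / 10 | 11 / 10 |
| ANTE(1) | 7 / 7 | 8 / 8 |
| TOEPH | 7 / 7 | 8 / 8 |
| TOEP | 4 / 4 | 5 / 4 |
| AR(1) | 2 / 2 | 3 / 3 |

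**Effect on the Week 26 contrast.** The fixed-effect estimates and their model-based standard errors depend on the covariance parameters only through V, so they cannot change. In three simulated trials (4 × 225 patients, about 3% dropout per visit), moving 0, 0.1 or 0.2 of variance from U to τ² changed nothing. In the first trial the −2 REML log-likelihood was 630.352481 each time, the contrast −0.34915 and the SE 0.0862. The smallest Hessian eigenvalue was about 282 to 369 for unstructured alone and about 1e-5 with the patient effect, which is the flat direction.

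Kenward-Roger is also unaffected in principle. Both versions are linear in their covariance parameters. Let A be the 10 × 11 map of rank 10 from the larger parameter set to the smaller, and I the information for the 10. Then A(A′IA)⁻A′ = I⁻¹ for any generalised inverse, so the adjustment is the same.

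**Does the fit complete?** In 100 simulated trials (12% dropout), plain unstructured converged in 100. With the patient effect added, scoring with a generalised inverse converged in 100, and the Week 26 estimate and SE differed from plain unstructured by at most 5e-10. Scoring that insists on an invertible information matrix converged in none, but that only restates the rank result: such an algorithm must fail on a matrix already known to be singular. It says nothing about the trial's software.

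**If the fallback were reached anyway.** AIC-chosen fallbacks without a patient effect were compared with unstructured in 40 trials for each of six settings: Week 26 SD 0.9; Week 4 SD 0.55, 0.70 or 0.90; correlations 0.45 to 0.78; dropout 12% or 25%. The SE ratio ranged from 0.954 to 1.030 in single trials, with setting means of 0.9875 to 1.0035. The largest shift in the estimate was 0.0088. Against the planned effect that is 0.0088/0.3 = 2.9%. Against the planned standard error, 0.9 × √(2/225) = 0.0849, it is about one tenth.

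**How the text resolves the wording.**
- SAP Section 3 bases the SAP on the analysis specified in Protocol Section 7, which has no random effect.
- SAP Section 4 lists departures from the protocol. It changes the back-up structures, and its visible text mentions no random patient effect.
- Section 4 also describes the back-ups as applying when the model fails with an unstructured structure. Plain unstructured is the step before the list, so its absence from the list is no gap.
- SAP 7.4.1 places the specified covariance in the residuals.
- SAP 7.5.1.2 to 7.5.1.4 write out the effects for weight, insulin dose and blood pressure under the same strategy, with no random patient effect.

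All of this fits one reading: patient identifies the subject within which the unstructured residual covariance applies.

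**The case for a change.** The best case for a change is that a confirmatory primary model should have exactly one reading, and this sentence admits two. A programmer who codes it literally fits a model whose information matrix is singular by construction, and completion then depends on the software. The SAP also does not say whether a patient effect would stay in the fallback models, where it would make TOEP redundant as well. Correcting the sentence would leave the estimand, alpha, data and sample size alone.

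The textual conflict and the redundancy stand. The harm does not. It needs a literal reading against the equation, the protocol and Section 4, then software that stops on the redundancy, then a statistician who moves to the fallback without fitting the plain unstructured model that both documents name. Even then the simulated effect is small. One gap in that evidence remains: the fallback simulations had no patient effect, so they do not bound a version that keeps one. In that version ANTE(1), TOEPH and AR(1) would still be identified.

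**Conclusion.** This is a slip of wording with no bearing on the result. If the fit completes, the primary efficacy and effectiveness contrasts equal those of plain unstructured. If a fallback without a patient effect were used, the standard error would lie within about 5% of unstructured in any one trial (setting means −1.3% to +0.4%), and the estimate would move by at most 0.009 against 0.3. Power and sample size are untouched.

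The rank result and the equality of a completed fit are algebra and need no assumption. The fallback sizes rest on the assumed correlations, SDs and dropout, and on REML code in Python; SAS, which the SAP specifies, was not tested. Some entries in SAP Section 4 are redacted, so a declared random effect there cannot be excluded, but it would not alter the algebra. Rewording the sentence would make the text tidier and change no analysis, so no change to the plan is called for.
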